**A. SPECIFIC AIMS**

*List the broad, long-term objectives and the goal of the specific research proposed, e.g., to test a stated hypothesis, create a novel design, solve a specific problem, challenge an existing paradigm or clinical practice, address a critical barrier to progress in the field, or develop new technology.*

**This study aims to evaluate the effectiveness of transcranial direct current stimulation (tDCS) and a brief cognitive intervention in increasing pain tolerance. Specifically, this study will determine whether healthy subjects will indicate greater pain tolerance to a heat stimulus following a single 20-minute session of anodal vs. cathodal tDCS (compared to sham tDCS). This study will also test whether providing one of four cognitive pain-managament interventions (conducted during the tDCS session) will result in even greater pain tolerance among subjects who also received tDCS .**

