**STUDY DESIGN AND PROCEDURES:**

Interested participants will call and be pre-screened on the telephone. If interested participants meet the inclusion criteria they will be scheduled for one appointment (lasting approximately 1 hour). Upon coming to the Brain Stimulation Laboratory for the appointment, participants will review and sign the informed consent document. Written informed-consent will be obtained by one of the study investigators or the study coordinator. Participants will complete the Center for Epidemiological Studies 10-item depression scale (CESD), the Beck Anxiety Inventory (BAI), the Reiss-Epstein-Gursky A.S.I., and the Brief Pain Inventory (BPI).

After completing the initial questionnaires they will be taken to the laboratory where they will undergo five trials of the heat tolerance laboratory pain test. The tDCS electrodes will then be placed and fastened with Velcro straps, and the tDCS session will be started. During the tDCS stimulation, participants will undergo the cognitive or educational component of the study as well as pain tolerance assessment procedures every 5 minutes. Patients will randomly receive one of four cognitive behavioral therapy interventions administered through headphones so that the research staff can remain blind. The four cognitive behavioral therapies include Pain-Catastrophizing Cognitive Intervention, Cognitive-Behavioral Distraction Intervention, Cognitively-Mediated Relaxation Intervention, Education-Only Control Condition.

After completion of the tDCS session, participants will again undergo five consecutive trials of the quantitative sensory testing.

At the completion of each appointment participants will be assessed for adverse effects of the stimulation, and they will be asked if they think they received real or fake stimulation and will rate how confident they are in their answer using a 0-10 scale (0= guessing 10= absolutely sure). Participants will also be asked to complete a short supplemental form at the end of the appointment. Participants will also be compensated \$40 in cash at that time for their participation in the study.

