**ANALYSIS:**

3 variable MANCOVA will be used to investigate whether change scores (from pre- to post-stimulation) in pain tolerance ratings (i.e., the temperature that participants were no longer able to tolerate the heat stimulus) are significantly affected by stimulation condition. Anodal, Cathodal, and Sham stimulation will be randomly paired with one of the four cognitive behavioral therapies. Both the stimulation and cognitive behavioral therapy will be run through a randomized computer system so as to maintain blinding. A 4X3X2 [CBT group BY tDCS group BY time (pre-post)] mixed multiple analysis of covariance (MANCOVA) will be conducted with the multiple QST values as dependent measures and while controlling for physiological indices across phases (pre- and post-intervention. Gender, age, and race will be controlled in all analyses, although specific demographic variable differences are not expected for the present study. Scores on initial tests (i.e., CESD, BAI, and BPI) may also be examined as control variables

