**We will collect CESD, BAI, BPI and laboratory pain ratings. All of the data will only contain a unique study identifier. The digital file containing identifying information will be kept on the PI locked and secure computer in 518-North, IOP at MUSC. All IRB approved study members will have access to the identifying information.**

c. Potential Risks

- Describe the potential risks to subjects (physical, psychological, social, legal, or other), and assess their likelihood and seriousness to the subjects.
- Where appropriate, describe alternative treatments and procedures, including the risks and benefits of the alternative treatments and procedures to participants in the proposed research.

tDCS has been found to be safe in humans with mild procedural side-effects such as tingling sensations under the sponge electrodes (experienced by 70% of tDCS patients), moderate fatigue (35%), and light itching sensations under the sponges (30%). After tDCS, the incidence of side-effects is lower but include headache (12%), nausea (3%) and insomnia (<1%) (Poreisz et al, 2007). If tDCS is delivered at 2mA for 20 minutes per day, every day for 4 or more days in a row, mild skin lesions have been reported. However, these lesions have all been reported to heal without scarring within 1 to 3 weeks following the end of tDCS treatment (Palm et al, 2008). Although there is no evidence to date that tDCS can cause seizures, there is a very minimal risk of seizures associated with tDCS. Qualified nurses and physicians are available 24 hours a day to handle any and all potential complications if they occur. The electrodes and configuration we intend to use in this study are believed to be safer and more comfortable than traditional sponge electrodes. There is also minimal risk of loss of confidentiality.

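### The 4X3X2 MANCOVA adjusts for unnamed physiological indices measured after both randomised interventions, so its adjusted effects need not be the total effects of assignment

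*Combined protocol and SAP*

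**What the plan says.** Section D, Analysis, describes the main model as follows: "A 4X3X2 [CBT group BY tDCS group BY time (pre-post)] mixed multiple analysis of covariance (MANCOVA) will be conducted". Its outcomes are the several QST measurements. The covariate clause of the same sentence reads: "while controlling for physiological indices across phases (pre- and post-intervention" (the parenthesis is never closed). The indices are therefore covariates, distinct from the QST outcomes, and they include post-intervention values. The other covariates in that section are fixed characteristics (gender, age, race) or questionnaires completed before treatment.

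The same section opens with what may be a separate analysis: "3 variable MANCOVA will be used to investigate whether change scores (from pre- to post-stimulation) in pain tolerance ratings" are affected by stimulation condition. No physiological covariate is mentioned there, and the plan does not say whether this is the same model.

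On timing, section D, Study Design and Procedures, states: "During the tDCS stimulation, participants will undergo the cognitive or educational component of the study". It then states: "After completion of the tDCS session, participants will again undergo five consecutive trials of the quantitative sensory testing".

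Section A asks whether tDCS raises tolerance compared with sham, and whether a cognitive intervention "will result in even greater pain tolerance among subjects who also received tDCS". It names no direct or mediated effect as the target.

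No physiological measure is described under Laboratory Pain Assessment or in the study procedures. The data list in section E.1.b reads: "We will collect CESD, BAI, BPI and laboratory pain ratings".

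**The concern.** Both factors are randomised, and the aims concern the effect of being assigned to a condition. A covariate measured after assignment may itself be changed by assignment. Conditioning on it removes any part of the effect that runs through the index. It can also create a spurious difference when index and outcome share an unmeasured cause. One of the four cognitive conditions is a relaxation intervention, so a shift in a physiological index is plausible, although the documents do not establish one.

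The 4X3X2 model is the only analysis that explicitly contains a CBT factor. The CBT and combined-treatment questions therefore have no other stated analysis, and no version limited to pre-intervention indices is given. Because the indices and their form of entry are unspecified, both could also be chosen after the data are seen.

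**Working it through.** **What the documents supply.** N = 360, three tDCS conditions and four cognitive conditions. Equal allocation (an assumption) gives 360/12 = 30 per cell, 90 per cognitive arm and 120 per tDCS arm. The plan gives no effect size, SD, alpha or power, so there is no figure to reproduce. Everything below is illustrative. It concerns single 1-df contrasts on one outcome at an assumed two-sided 5% level, not the planned multivariate test.

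**Model.** D is the pre-to-post change in the outcome (SD 1), so a group effect on D is the group-by-time effect. The pre index is M0 ~ N(0,1). The post index is M1 = 0.75·M0 + e + shift, with e ~ N(0,1). The outcome is D = true effect + r·e + √(1−r²)·u.

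The raw SD of M1 is √(0.5625 + 1) = 1.25, and its correlation with M0 is 0.75/1.25 = 0.6. The shift is in conditional SD units (post given pre), so 0.8 is 0.8/1.25 = 0.64 raw SD.

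**Formulas.**
- Adjusted estimate = true effect − shift × r.
- SE with the pre index only, 90 v 90: √(2/90) = 0.149.
- SE with the post index added: about √(1−r²) × √(2/90 + shift²/347).

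**CBT contrast, true effect 0.40.** With the pre index only, 0.40/0.149 = 2.68, which is power of about 76%. With the post index added (simulation of the full 12-cell model, 4,000 replicates):

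| Shift, r | Arithmetic | Estimate | Power |
|---|---|---|---|
| 0, 0.3 | 0.40 − 0 | 0.40 | 80% |
| 0, 0.5 | 0.40 − 0 | 0.40 | 87% |
| 0.3, 0.3 | 0.40 − 0.09 | 0.31 | 59% |
| 0.5, 0.4 | 0.40 − 0.20 | 0.20 | 30% |
| 0.8, 0.5 | 0.40 − 0.40 | 0.00 | 5% |
| −0.5, 0.4 | 0.40 + 0.20 | 0.60 | 99% |

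Worked example, shift 0.5 and r 0.4: SE = 0.917 × √(0.0222 + 0.0007) = 0.139, and 0.20/0.139 = 1.44, which is power of about 30%. The zero in the 0.8, 0.5 row arises because 0.8 × 0.5 equals the assumed effect. It marks the extreme of the range.

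**No true total effect.** For the CBT contrast the test rejects in 9% of trials (shift 0.3, r 0.3) or 30% (0.5, 0.4). For a tDCS contrast, 120 v 120, with a tDCS shift of 0.5 and r 0.4, it rejects in 37%.

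**CBT-by-tDCS interaction contrast, true value 0.40.** The SE is √(4/30) = 0.365 and power is 19% with the pre index only. A CBT shift equal in all tDCS arms leaves the estimate at 0.39 to 0.40. If the shift differs by 0.5 between combinations (r 0.4), the estimate is 0.19 with power 9%, or 0.60 with the opposite sign.

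**Form of entry (CBT contrast, shift 0.5, r 0.4).**
- Separate pre and post values: 0.20.
- Time-varying: the slope is 0.4/1.0625 = 0.376, and 0.40 − 0.5 × 0.376 = 0.21.
- Pre-post average with a covariate-by-time term: the slope is 0.2/1.0156 = 0.197, and 0.40 − 0.25 × 0.197 = 0.35.
- Average without that term: 0.40, no bias.

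**A different data model.** A two-arm simulation (90 per arm, 2,000 runs) let the index act on the outcome directly with slope b, or share an unmeasured cause with it. With an index shift of 0.5 SD, a true 0.40 became 0.25 (b = 0.3), 0.15 (b = 0.5), or 0.23 (b = 0, shared cause with loading 0.5). With a shifted index unrelated to the outcome, the estimate stayed at 0.40 and only precision was lost. Dropping the post index returned the estimate to the total effect in every scenario.

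**The case against.** The strongest reply is that the harm rests on stacked conditions that the documents do not establish. No index is scheduled, none is shown to respond to treatment, and none is shown to relate to the outcome. The loose wording leaves open an averaged covariate without a time term, which causes no bias. All of this is correct and limits the claim to a conditional one. It does not rescue the clause: if an index is recorded, the model risks bias, and if none is, the model cannot be fitted as written. Absence from section E.1.b is not proof that nothing is recorded, because that list also omits the anxiety sensitivity scale collected at the visit.

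Second, the opening change-score MANCOVA carries no stated physiological covariate. If it is a separate analysis, the tDCS-versus-sham question has an analysis free of this problem, and the exposure falls on the CBT and combination questions. That stands, but the plan does not settle whether the two are separate.

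Third, the 4X3X2 outcomes are the QST values, while the aims speak of heat tolerance. This matters little, since the procedures describe the post-session repeat as again being quantitative sensory testing.

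Finally, the magnitudes are arithmetic on assumed inputs. They also make the pre index unrelated to outcome change, so the precision cost quoted is specific to that choice. They show what could happen and do not predict what will.

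**Conclusion.** The point holds as a conditional one. The plan includes post-intervention covariates in the only model that explicitly has a CBT factor, while the aims ask for the effect of assignment. If a recorded index enters with phase-specific values, is shifted by a randomised condition and is related to outcome change, that factor's group-by-time effect is biased by shift × r. Over the assumed ranges (shift 0 to 0.8 conditional SD, r 0.3 to 0.5) this is 0 to 0.40 SD in either direction. The interaction is biased only where the shift differs between CBT-tDCS combinations. If any condition fails, there is no bias from this source. The matter should be fixed, with medium confidence about its practical effect because the indices are unnamed.

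**What to change.** In the 4X3X2 model, remove post-intervention and time-varying physiological covariates. If physiological indices are recorded, name them, state when they are measured, and adjust only for pre-intervention values. If none is recorded, delete the clause. State whether the opening three-variable MANCOVA is the same model and, if so, apply the same rule. Analyse post-intervention physiology separately, as an outcome or as a labelled exploratory mediation analysis.

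This costs about one sentence of analysis wording and no new data. The price is some precision if treatment does not move the index: in the illustration, about 76% power with the pre index only, against 80% to 87% with the post index added.

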**E. PROTECTION OF HUMAN SUBJECTS**

---

**1. RISKS TO THE SUBJECTS**

*a. Human Subjects Involvement and Characteristics*

- *Describe the proposed involvement of human subjects.*
- *Describe the characteristics of the subject population, including their anticipated number, age range and health status.*

Participants will be 360 healthy adult volunteers

### Targeted/Planned Enrollment Table

Total Planned Enrollment 360

TARGETED/PLANNED ENROLLMENT: Number of Subjects			
Ethnic Category	Sex/Gender		
	Females	Males	Total
Hispanic or Latino	9	8	18
Not Hispanic or Latino	183	159	342
Ethnic Category: Total of All Subjects*	360		
Racial Categories			
American Indian/Alaska Native	10	10	20
Asian	14	11	25
Native Hawaiian or Other Pacific Islander	0	0	0
Black or African American	65	55	120
White	110	85	195
Racial Categories: Total of All Subjects*	199	161	360

\*The "Ethnic Category: Total of All Subjects" must be equal to the "Racial Categories: Total of All Subjects".

- Identify the criteria for inclusion or exclusion of any subpopulation.
- Explain the rationale for the involvement of special classes of subjects, such as fetuses, neonates, pregnant women, children, prisoners, institutionalized individuals, or others who may be considered vulnerable populations. Note that 'prisoners' includes all subjects involuntarily incarcerated (for example, in detention centers) as well as subjects who become incarcerated after the study begins.
- If you propose to exclude any sex/gender or racial/ethnic group, include a compelling rationale for the proposed exclusion. For example, 1) the research question addressed is relevant to only one gender or 2) evidence from prior research strongly demonstrates no difference between genders.
- Provide either a description of the plans to include children or, if children will be excluded from the proposed research, then you must present an acceptable justification for the exclusion. For example, 1) the condition is rare in children as compared to adults or 2) insufficient data are available in adults to judge risk in children.
- List any collaborating sites where human subjects research will be performed, and describe the role of those sites in performing the proposed research.

N/A

b. Sources of Materials

- Describe the research material obtained from living human subjects in the form of specimens, records, or data.
- Describe any data that will be recorded on the human subjects involved in the project.
- Describe the linkages to subjects, and indicate who will have access to subject identities.
- Provide information about how the specimens, records, or data are collected and whether material or data will be collected specifically for your proposed research project.

**We will collect CESD, BAI, BPI and laboratory pain ratings. All of the data will only contain a unique study identifier. The digital file containing identifying information will be kept on the PI locked and secure computer in 518-North, IOP at MUSC. All IRB approved study members will have access to the identifying information.**

c. Potential Risks

- Describe the potential risks to subjects (physical, psychological, social, legal, or other), and assess their likelihood and seriousness to the subjects.
- Where appropriate, describe alternative treatments and procedures, including the risks and benefits of the alternative treatments and procedures to participants in the proposed research.

tDCS has been found to be safe in humans with mild procedural side-effects such as tingling sensations under the sponge electrodes (experienced by 70% of tDCS patients), moderate fatigue (35%), and light itching sensations under the sponges (30%). After tDCS, the incidence of side-effects is lower but include headache (12%), nausea (3%) and insomnia (<1%) (Poreisz et al, 2007). If tDCS is delivered at 2mA for 20 minutes per day, every day for 4 or more days in a row, mild skin lesions have been reported. However, these lesions have all been reported to heal without scarring within 1 to 3 weeks following the end of tDCS treatment (Palm et al, 2008). Although there is no evidence to date that tDCS can cause seizures, there is a very minimal risk of seizures associated with tDCS. Qualified nurses and physicians are available 24 hours a day to handle any and all potential complications if they occur. The electrodes and configuration we intend to use in this study are believed to be safer and more comfortable than traditional sponge electrodes. There is also minimal risk of loss of confidentiality.

## 2. ADEQUACY OF PROTECTION AGAINST RISKS

### a. Recruitment and Informed Consent

- *Describe plans for the recruitment of subjects (where appropriate) and the process for obtaining informed consent. If the proposed studies will include children, describe the process for meeting requirements for parental permission and child assent.*
- *Include a description of the circumstances under which consent will be sought and obtained, who will seek it, the nature of the information to be provided to prospective subjects, and the method of documenting consent.*

PI and research assistant will advertise the study via flyers around the MUSC campus. Interested participants will call and be initially screened on the telephone. Participants will be excluded if they have any chronic pain conditions, seizures, a family history of a seizure disorder, are suicidal, have implanted metal devices (e.g., pacemakers, metal plates, wires), are pregnant, have history of brain surgery or history of loss of consciousness >15 minutes, are taking any medication associated with lowered seizure threshold, or are allergic to latex. Written consent to participate will be obtained in a private office in the Brain Stimulation Laboratory at MUSC.

### b. Protection against Risk

- *Describe planned procedures for protecting against or minimizing potential risks, including risks to confidentiality, and assess their likely effectiveness.*
- *Where appropriate, discuss plans for ensuring necessary medical or professional intervention in the event of adverse effects to the subjects.*
- *Studies that involve clinical trials (biomedical and behavioral intervention studies) must include a description of the plan for data and safety monitoring of the research and adverse event reporting to ensure the safety of subjects in Section 4 below.*

**The study will take place in IOP and qualified nurses and physicians will be available 24 hours a day to handle any and all potential complications if they occur.**

## 3. POTENTIAL BENEFITS OF THE PROPOSED RESEARCH TO THE SUBJECTS AND OTHERS

- *Discuss the potential benefits of the research to the subjects and others.*
- *Discuss why the risks to subjects are reasonable in relation to the anticipated benefits to subjects and others.*

**There are no anticipated direct benefits to participants.**

## 4. IMPORTANCE OF THE KNOWLEDGE TO BE GAINED

- *Discuss the importance of the knowledge gained or to be gained as a result of the proposed research.*
- *Discuss why the risks to subjects are reasonable in relation to the importance of the knowledge that reasonably may be expected to result.*
- *NOTE: Test articles (investigational new drugs, devices, or biologicals) including test articles that will be used for purposes or administered by routes that have not been approved for general use by the Food and Drug Administration (FDA) must be named. State whether the 30-day interval between submission of applicant certification to the FDA and its response has elapsed or has been waived and/or whether use of the test article*

has been withheld or restricted by the Food and Drug Administration, and/or the status of requests for an IND or IDE covering the proposed use of the test article in the research plan.

Chronic pain is a huge public health concern and more treatment options are needed. It is believed that the information gained through this investigation might help us determine the feasibility of tDCS in combination with cognitive interventions as a treatment option for certain types of pain.

## 5. SUBJECT SAFETY AND MINIMIZING RISKS (Data and Safety Monitoring Plan)

*Studies that involve \*clinical trials (see description below) must include a description of the plan for subject safety and minimizing risks of the research, including data monitoring and adverse event reporting to ensure the safety of subjects. The complexity of the plan should be determined by the level of risk to subjects. The plan should specify: 1) what will be monitored, 2) how frequently the monitoring will occur, 3) who will be responsible for the monitoring, and 4) study endpoints.*

Participants will be carefully monitored for the entirety of the study. Any adverse events will be recorded and reviewed by the PI. Applicable cases will be reported to the IRB according to the IRB policy. This data will also be used to further establish the safety profile of tDCS in the current research literature.

